## 8.4 Discontinuation from the Study

---

A subject's study participation may be discontinued at any time if, in the opinion of the Sponsor or the investigator, it is in the best interest of the subject. All discontinuations will be fully documented on the appropriate study forms and a discontinuation/exit form will be completed.

## 9 Device Deficiency Reporting

---

### 9.1 Product Defect Reporting (Investigator Responsibility)

---

Product Defect is the terminology typically used in contact lens products for an *unexpected* observation related to the identity, quality, durability, reliability, or usability of the product under investigation.

NOTE: Observations on study products that are anticipated as a part of the device development process are not considered to be Product Defects or Device Deficiencies.

If the Product Defect is associated with an adverse event, the investigator shall report the Product defect via the Adverse Event Notification Form (Appendix 1).

If the Product Defect is not associated with an adverse event, the investigator shall report the Product Defect via the Clinical Product Defect Notification Case Report Form (Appendix 2).

If the investigator judges that the Product Defect could have led to a Serious Adverse Event if no preventative action was taken, the Product Defect should be reported to the Sponsor via the Product Defect Notification Case Report Form within 24 hours of becoming aware of the defect. The investigator should report to the IRB per their reporting requirements.

All other Product Defects should be reported to CVI as soon as possible, but no later than 5 working days after occurrence.

Sponsor contact details for Product Defect Notifications are:

Contact: Clinical Operations, CooperVision  
Email: [[contact]](mailto:[contact])  
Address: [name]  
[name]

## 9.2 Device Deficiency Reporting (Sponsor Responsibility)

---

Device Deficiency is defined as the inadequacy of a medical device with respect to its identity, quality, durability, reliability, usability, safety or performance.

The Sponsor will review the Product Defect Notification Case Report Form, gather additional information if needed from the Investigator and determine whether the notification represents a Device Deficiency. Device Deficiencies will be reported as per Internal CVI procedures.

A summary of Device Deficiencies will be documented in the clinical study report. If no Device Deficiencies are observed in a study, then a statement stating as such will be included in the clinical study report.

## 10 Statistical Design and Analysis

---

### 10.1 Statistical Hypothesis

---

In this confirmatory study, the primary statistical hypothesis is that the logMAR visual acuity performance with the Test lens will demonstrate there is no statistical difference comparing to the Control lens over one month of lens wear.

The null and alternative hypotheses are:

$$H_0: \mu_t = \mu_c$$

$$H_1: \mu_t \neq \mu_c$$

Where  $\mu_t$  refers to the LogMAR of Test lenses and  $\mu_c$  refers to LogMAR of Control lenses.

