# Overall Synopsis of the Clinical Investigation Plan (Protocol)

Sponsor Address:	[REDACTED]
Funding Source:	CooperVision Intl Ltd – For more details, see Study Agreements
Investigation Sites:	See Appendix 13
Principal Investigators:	See Appendix 13
Protocol Synopsis:	The objective of this study is to confirm the clinical performance of two different manufacturing processes for comfilcon A contact lenses.
Planned Start Date	Nov 2023
Estimated Duration	4 months
Primary Study Objective	To assess the clinical performance of comfilcon A lenses
Overview of Study Design	30 day refit, parallel arm of comfilcon A with a novel process (Test) vs comfilcon A with the current process (Control)
Primary Outcome(s)	logMAR visual acuity
Secondary Outcome(s)	None
Visit Schedule	Baseline & Dispensing, 1-week, 4-weeks
Study Products	Supplied by the Sponsor
Subject Population	# of subjects: A maximum of 79 subjects will be enrolled in order to achieve a minimum of 72 completed subjects Adults (mix of symptomatic and asymptomatic)
Inclusion/Exclusion	Main Inclusion criteria: Standard inclusion criteria Main Exclusion criteria: Standard exclusion criteria

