### 7.3 Subjects

---

A maximum of 79 subjects will be enrolled in this study in order for approximately 72 to complete the study. Each subject will be given a unique ID number. ID numbers will not be re-used. All subjects must meet the study inclusion and exclusion criteria listed below.

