### 10.2 Sample Size Calculations

---

The number of subjects that has been chosen in this study is to provide sufficient evidence to demonstrate the study hypothesis of “there is no difference between the Test and Control” versus “there is a difference between the Test and Control” on visual acuity (LogMAR) measurement. With assumed standard deviation is equal to 0.06, a sample size of 24 subjects per group will provide adequate power (92%) to detect a visual acuity difference of 0.06 (3 letters) at  $\alpha=0.05$  level.

Therefore, for this parallel arm study design with 2:1 ratio, minimum 72 subjects (48 in test arm and 24 in control arm) to complete is required. To account for subject attrition of 10%, up to 79 subjects will be enrolled in this study.

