## **10.3 Statistical Analysis**

---

Statistical analysis will be undertaken by the study biostatistician. Data for all subjects who have completed the trial will be included in the analysis.

Descriptive statistics (e.g., mean, standard deviation) and/ or frequency of counts for categorical data may be produced for primary and/or second interests. Paired t-test may be used to compare slit lamp biomicroscopy, lens fit and subjective scores between study lens types. Where applicable, Repeated Measures Analysis of Variance (ANOVA) or paired analysis may be used to compare the variables between study visits. The critical alpha level for statistical significance will be set at  $p \leq 0.05$ , with adjustment for multiple comparisons.

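### The plan sets out to demonstrate no difference in acuity but makes equality the null hypothesis, with no margin, confidence-interval rule or named between-arm test, so the claim can rest only on a non-significant result

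*Combined protocol and SAP*

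**What the plan says.** Section 10.1 describes the study as confirmatory. Its primary hypothesis reads: "the logMAR visual acuity performance with the Test lens will demonstrate there is no statistical difference comparing to the Control lens". The period in question is one month. The formal statement is H0: μt = μc against H1: μt ≠ μc, so the conclusion the sponsor wants is the null.

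Section 10.2 keeps that arrangement. The sample is meant "to provide sufficient evidence to demonstrate the study hypothesis of" no difference, but the power quoted (92% with 24 per group) is power to detect a difference of 0.06 logMAR, or 3 letters, at α = 0.05. "With assumed standard deviation is equal to 0.06" is the only variability input. With 2:1 allocation, "minimum 72 subjects (48 in test arm and 24 in control arm) to complete is required". The Synopsis likewise enrols "in order to achieve a minimum of 72 completed subjects", whereas Section 7.3 says "in order for approximately 72 to complete the study".

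Section 10.3 sets significance at p ≤ 0.05 and lists methods. "Paired t-test may be used to compare slit lamp biomicroscopy, lens fit and subjective scores between study lens types"; acuity is not in that list. Repeated-measures ANOVA or paired analysis "may be used to compare the variables between study visits", which is a comparison over time and not between arms. For the primary endpoint, acuity at 4 weeks (Sections 1 and 7.1), no between-arm test is named. No section gives an equivalence or non-inferiority margin, a confidence-interval rule or a success criterion.

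**The concern.** A non-significant test of equality shows that the data did not exclude zero. It does not show that they excluded a difference that matters. The plan never says outright that p > 0.05 means success, but its hypotheses and its single threshold leave no other route to the stated claim.

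Such a rule errs in two directions. Noisier data or fewer completers make no difference easier to reach, so poor precision is rewarded. Precise data can reject equality over a difference small enough to be acceptable, so the sponsor may fail a lens that is in fact similar. The Synopsis lists no secondary outcomes, so the study's one declared conclusion depends on this rule.

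**Working it through.** **Inputs.** From Section 10.2: SD 0.06, difference 0.06, α = 0.05, 24 per group for the power statement, 48:24 completers, 10% attrition, up to 79 enrolled. H1 in Section 10.1 is two-sided. Assumptions made here: one acuity value per subject; SDs above 0.06; ±0.06 as an illustrative margin, because it is the only difference the plan names.

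**1. The plan's figure.** Two-sample t-test, SE = SD × √(1/n₁ + 1/n₂), power from the noncentral t distribution.
- 24:24: SE = 0.06 × √(1/24 + 1/24) = 0.0173; power 92.4%. The stated 92% reproduces, as the power of a test for a difference.
- 48:24: SE = 0.06 × √(1/48 + 1/24) = 0.015; power 97.6%.

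**2. Chance of a non-significant result when the true difference is 0.06** (1 − power).

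| Completers | SD | Non-significant |
|---|---|---|
| 48:24 | 0.06 | 2.4% |
| 48:24 | 0.07 | 7.8% |
| 48:24 | 0.08 | 16% |
| 48:24 | 0.10 | 34% |
| 47:24 (10% loss from 79) | 0.06 | 2.4% |
| 40:20 (24% loss) | 0.06 | 5.2% |
| 32:16 (39% loss) | 0.06 | 11% |

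Power of 92% survives at 48:24 up to an SD of about 0.070, or at SD 0.06 down to 54 completers (36:18). The SD therefore matters more than attrition.

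**3. Example: noise helps the claim.** 48:24, SD 0.08, observed difference 0.035. SE = 0.08 × √(1/48 + 1/24) = 0.020; t = 0.035/0.020 = 1.75; p = 0.08. The 90% interval is 0.035 ± 1.667 × 0.020 = 0.002 to 0.068. The result is non-significant, yet the data do not exclude 0.06.

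**4. Example: precision hurts the claim.** 48:24, SD 0.06, observed difference 0.032. t = 0.032/0.015 = 2.13; p = 0.036. The 90% interval is 0.032 ± 1.667 × 0.015 = 0.007 to 0.057, inside ±0.06, yet the stated hypothesis fails.

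**5. How often the second error occurs.** 48:24, SD 0.06, true difference 0.02 (one letter on the plan's scale): p ≤ 0.05 in 26% of trials. The result is significant and the interval still lies within ±0.06 in 10.6% of trials with a 90% interval, or 4.7% with a 95% interval.

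**6. Power of an interval rule at ±0.06** (integrating over the sample SD).

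| Completers | SD | True difference | 90% interval | 95% interval |
|---|---|---|---|---|
| 48:24 | 0.06 | 0 | 98% | 95% |
| 48:24 | 0.06 | 0.02 | 84% | 75% |
| 48:24 | 0.08 | 0 | 82% | 68% |
| 48:24 | 0.10 | 0 | 54% | 32% |
| 40:20 | 0.06 | 0 | 95% | 90% |
| 32:16 | 0.06 | 0 | 88% | 78% |

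If the true difference equals the margin, the 90% rule declares similarity in at most 5% of trials, whatever the SD or number of completers. At 48:24 and SD 0.06 the figures are 5.0% (90% interval) and 2.5% (95% interval).

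**The case against.** The strongest reply is that at the plan's own design the two rules nearly coincide. With 48:24 and an observed SD of 0.06, a non-significant result requires an absolute difference below 1.994 × 0.015 = 0.0299, so its 95% interval ends below 2 × 0.0299 = 0.0598, just inside ±0.06. A 90% interval rule is in fact looser there: 5.0% false similarity against 2.4%. The larger miss rates need SDs that the plan does not contain, or losses of 24% to 39% against a planned 10%. The opposite error depends on the margin and interval level chosen: with a 95% interval, the example in step 4 gives 0.032 ± 0.0299 = 0.002 to 0.062, and both rules fail the lens. The missing test could be inferred, since the 92% is that of a two-sample t-test. The stakes are also modest: both lenses are listed as approved, and the subjects already wear comfilcon A.

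All of this is arithmetically right, and it limits the size of the problem. It does not repair the rule. The protection comes from the assumed SD, for which Section 10.2 gives no source, and from the number completing. Nothing in the decision rule restores it if either falls short. The opposite error needs no adverse assumption about SD or attrition, and it still occurs in 4.7% of trials with a 95% interval at a true difference of 0.02, although a tighter margin would all but remove it. An inferable test is not a specified one, and it would still leave no criterion for concluding similarity.

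**Conclusion.** The concern holds. The plan presents a confirmatory claim of no difference, and its hypotheses and threshold can support that claim only by non-rejection. This is an error in the decision rule and not merely missing detail, and it affects the only declared outcome, so it should be corrected before the analysis.

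The case rests on the logic of the claim and not on a likely wrong verdict at the design assumptions, where the risk of missing 0.06 is 2.4%. The 16% and 34% miss rates rest on assumed SDs of 0.08 and 0.10. The 10.6% (or 4.7%) rests on a true difference of 0.02 and on ±0.06 being acceptable, which the plan does not state. All figures take one acuity value per subject.

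**What to change.** - **Section 10.1:** restate as H0: |μt − μc| ≥ margin against H1: |μt − μc| < margin, or as one-sided non-inferiority if only worse acuity matters for the objective in Section 1. The sponsor should justify the margin clinically; 0.06 logMAR is a candidate only because the plan already names it.
- **Section 10.3:** name one primary analysis, a confidence interval for Test minus Control in 4-week logMAR acuity. Fix the level in advance: 90%, which equals two one-sided tests at the plan's 0.05, or 95%. Section 7.5.3 measures acuity in each eye separately, so use one value per subject or a model that allows for two eyes. Conclude similarity only if the whole interval lies within the margin (for non-inferiority, only if the relevant limit does).
- **Section 10.2:** restate power for that test. At ±0.06, 48:24, SD 0.06 and no true difference it is about 98% (90% interval) or 95% (95% interval); non-inferiority at one-sided 0.025 gives about 98%.

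The cost is the wording of three sections and a margin justification. No extra subjects are needed if ±0.06 is justified, the SD is near 0.06 and the true difference is near zero. The drawback is that the interval rule loses power in the same adverse cases where it protects, as the last table shows. With a 0.04 margin at 48:24, SD 0.06 and no true difference, power is 68% (90% interval) or 50% (95% interval), so a tighter margin or a larger SD would need more subjects.

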### 10.2 Sample Size Calculations

---

The number of subjects that has been chosen in this study is to provide sufficient evidence to demonstrate the study hypothesis of “there is no difference between the Test and Control” versus “there is a difference between the Test and Control” on visual acuity (LogMAR) measurement. With assumed standard deviation is equal to 0.06, a sample size of 24 subjects per group will provide adequate power (92%) to detect a visual acuity difference of 0.06 (3 letters) at  $\alpha=0.05$  level.

Therefore, for this parallel arm study design with 2:1 ratio, minimum 72 subjects (48 in test arm and 24 in control arm) to complete is required. To account for subject attrition of 10%, up to 79 subjects will be enrolled in this study.

## **10.3 Statistical Analysis**

---

Statistical analysis will be undertaken by the study biostatistician. Data for all subjects who have completed the trial will be included in the analysis.

Descriptive statistics (e.g., mean, standard deviation) and/ or frequency of counts for categorical data may be produced for primary and/or second interests. Paired t-test may be used to compare slit lamp biomicroscopy, lens fit and subjective scores between study lens types. Where applicable, Repeated Measures Analysis of Variance (ANOVA) or paired analysis may be used to compare the variables between study visits. The critical alpha level for statistical significance will be set at  $p \leq 0.05$ , with adjustment for multiple comparisons.

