## 2 Study Design

---

This will be a prospective, multiple day, double (investigator and subject)-masked, randomized, bilateral re-fit parallel arm study comparing a Test lens against an appropriate Control lens. Subjects will be randomized to wear the Test or Control lens for  $30\pm 2$  days. There will be an interim visit after  $7\pm 1$  days of lens wear. Subjective questionnaires will also be collected over the duration of lens wear.

There will be a total of 3 visits in the study as described in Section 7.5 below.

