## 4 Justification for the Study Design

---

Nonclinical testing methods are not adequate to provide the information needed to advance the development of the comfilcon A Contact Lens. A biocompatibility assessment has been completed and the benefit/risk assessment (see Section 5 below) supports the use of the device in this study.

A parallel-group study design has been chosen given the length of the study and to minimize recall bias in determining subjective preference.

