#### 7.4.2 Randomization Procedures

In this parallel group study design, subjects will be randomized to wear either the Test or the Control lens in a bilateral fashion according to a predetermined randomization schedule. Test lenses will be dispensed at a ratio of two for every one Control lens. To maintain masking, Test lenses will be randomized as two of the three groups used in the study. The randomization will be performed using a randomization algorithm using REDCap Cloud.

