### 7.5.3 Visit 3 – 4 Week Visit (Day 30±2)

- Subject will arrive after wearing the lenses for at least 5 hours.
- Monocular logMAR visual acuity will be performed.

- LogMAR visual acuity with spectacles or spectacle refraction.
- The subject will be discharged and will sign the exit statement.

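### Section 10.3 offers a paired t-test for comparing Test and Control on slit lamp, lens fit and subjective scores, but the parallel-arm design yields no Test-Control pairs

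*Combined protocol and SAP*

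**What the plan says.** On the method, section 10.3 states: "Paired t-test may be used to compare slit lamp biomicroscopy, lens fit and subjective scores between study lens types". A separate sentence covers change over time: repeated-measures ANOVA or "paired analysis may be used to compare the variables between study visits". On the analysis set, the same section says: "Data for all subjects who have completed the trial will be included in the analysis".

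On the design, section 2 describes a "randomized, bilateral re-fit parallel arm study comparing a Test lens against an appropriate Control lens". Section 7.4.2 says "subjects will be randomized to wear either the Test or the Control lens in a bilateral fashion", with two Test allocations for each Control. Section 4 shows that this was deliberate: "A parallel-group study design has been chosen given the length of the study and to minimize recall bias in determining subjective preference". Section 10.2 gives the planned numbers: "minimum 72 subjects (48 in test arm and 24 in control arm) to complete is required".

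On the status of the scores, sections 1 and 7.1 list 4-week logMAR acuity as the only endpoint, and the synopsis lists no secondary outcomes.

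**The concern.** A paired t-test works on within-pair differences. To compare lens types, each pair must contain one Test value and one Control value from the same person, from fellow eyes, or from deliberately matched people. The design described in sections 2, 4 and 7.4.2 provides none of these.

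Slit lamp findings, lens surface and fit, and subjective assessments are scheduled at all three visits (Table 2), so comparisons of the two manufacturing processes on them are likely to be reported. If the named test does not fit, the analyst has to choose another test when the data are in hand, and must also decide whether the eye or the subject is the unit. A plan should settle both beforehand.

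**Working it through.** **Step 1: look for a source of Test-Control pairs.**

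- Same subject, both lenses: no. Each subject wears Test or Control for the whole 30 ± 2 days (section 2).
- Fellow eyes: no. Wear is bilateral with one lens type (section 7.4.2).
- Matched subjects: no. Section 7.4.2 describes randomization from a predetermined schedule and mentions no matching.
- The three labels A, B and C: no. They mask two Test groups and one Control group made up of different subjects (section 3.1, Table 1).
- Study lens against habitual lens: every subject is a habitual comfilcon A wearer and there is a habitual questionnaire, so such a within-subject comparison is possible. However, the sentence concerns study lens types, and Table 1 lists those as Test and Control.
- Visit against visit: this pairing is valid, but section 10.3 covers it in its own sentence.

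No reading produces pairs. Section 10.3 shows no redaction that could hide one.

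**Step 2: reproduce the plan's power figure.** Inputs from section 10.2: difference 0.06 logMAR, SD 0.06, 24 per group, alpha 0.05. The hypotheses in section 10.1 imply a two-sided test.

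- Independent two-sample t-test: SE = 0.06 × √(1/24 + 1/24) = 0.0173. Noncentrality = 0.06/0.0173 = 3.46 on 46 df. Power = 92.4%, against the stated 92%.
- Paired t-test on 24 pairs with zero correlation: SD of differences = 0.06 × √2 = 0.0849. SE = 0.0849/√24 = 0.0173, so the noncentrality is again 3.46, now on 23 df. Power = 91.2%.

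The stated power agrees with independent groups but does not prove that basis by itself. The conclusion rests on the design text in step 1.

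**Step 3: what a fitting test delivers on these scores.** The plan gives no SD for them, so the result is in SD units. With 48 Test and 24 Control completers:

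- SE of the difference = SD × √(1/48 + 1/24) = SD × √0.0625 = 0.25 SD, on 70 df.
- The difference d is the value at which a noncentral t with noncentrality d/0.25 gives the required power at two-sided 0.05.
- 80% power: d = 0.71 SD. 90% power: d = 0.82 SD.

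These figures precede the multiplicity adjustment that section 10.3 mentions. They describe the remedy and do not measure harm from the present wording.

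**The case against.** The strongest reply is that little depends on this sentence. It says only that the test may be used, so the biostatistician can choose an independent-groups test without departing from the plan. Section 10.3 also allows descriptive statistics and frequency counts, so the scores are not left without any analysis. They are not declared endpoints, and no stated conclusion depends on them. All of this stands, and it keeps the point modest. It does not make the sentence right: a permissive verb cannot make an inapplicable test applicable, and no other inferential method is named for comparing the lenses on these scores.

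A reader might infer three stronger things that the documents do not support.

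- **That a third of completers would be lost.** One-to-one pairing of 48 with 24 would leave out 48 − 24 = 24 of 72 (33%). That assumes an arbitrary matching of unrelated subjects, which the plan never proposes. The defect would be the same under 1:1 allocation.
- **That the primary comparison is compromised.** The sentence lists slit lamp, fit and subjective scores and does not mention acuity. Section 10.3 does not name the between-arm test for logMAR, but that is a missing detail and a separate matter. The two-mean hypotheses in section 10.1 and the per-group sizing in section 10.2 already point to independent groups.
- **That the trial must be resized.** The two-sample calculation in step 2 of the working reproduces the stated power on the plan's own inputs. The same test at 48 and 24 has noncentrality 0.06/(0.25 × 0.06) = 4 and power 97.6%.

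**Conclusion.** The point holds in a limited form. The paired t-test between study lens types is wrong for this design as written; this is more than a missing detail, because no Test-Control pairs exist. It is worth correcting but not serious: it touches permissively worded analyses of scores that are not endpoints, and leaves the primary logMAR comparison and the sample size intact.

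No numerical loss can be attached to the error itself. The 0.71 SD detectable difference (80% power) assumes 48 and 24 completers, equal variances, roughly normal scores and one value per subject. Graded scales may not meet the normality assumption. The conclusion about pairing needs none of these assumptions and follows from sections 2, 4 and 7.4.2.

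**What to change.** In section 10.3:

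1. Replace the paired t-test between lens types with an independent-groups test on all completers: a two-sample or Welch t-test for approximately continuous scores, and a rank-sum test or ordinal model for graded scales.
2. State that the subject is the unit of analysis where both eyes are scored, using either the mean of the two eyes or a model with eyes nested in subject.
3. Confine paired and repeated-measures methods to comparisons between visits.

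The cost is a wording change. It needs no extra subjects, visits or measurements.

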#### 7.3.1 Inclusion Criteria

A person is eligible for inclusion in the study if they:

- Have had a self-reported oculo-visual examination in the last year.
- Are at least 18 years of age and has full legal capacity to give their informed consent.
- Have read and understood the informed consent form.
- Are willing and able to follow instructions and maintain the appointment schedule.
- Have a contact lens spherical prescription between -0.50 D to -6.00 D (inclusive)
- Are correctable to a visual acuity of 20/40 or better (in each eye) with their habitual vision correction or 20/20 best-corrected.
- Have spectacle cylinder of  $\leq 0.75$  D in both eyes.
- Is a habitual comfilcon A wearer and worn a comfilcon A lens for at least one month (minimum of 8 hours a day, 5 days per week)
- Currently employ the use of a peroxide or multipurpose solution cleaning and disinfecting regimen in one of the following brand names:

- Bausch and Lomb BioTrue Multi-Purpose Solution
- Bausch and Lomb BioTrue Hydration Plus Multi-Purpose Solution
- Bausch and Lomb ReNu Advanced Formulation Multi-Purpose Solution
- Alcon Opti-Free Puremoist with Hydraglyde Multi-Purpose Solution
- Alcon Opti-Free Replenish Multi-Purpose Solution
- Alcon Clear Care Plus Hydrogen Peroxide Solution
- Acuvue RevitaLens Multi-Purpose Solution
- Have clear corneas and no active ocular disease.
- Have not worn habitual lenses for at least 12 hours before the baseline/screening examination
- Are willing to wear the study contact lenses for at least 8 hours per day, 5 days per week

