### 7.5.2 Visit 2 – 1 Week Visit (Day 7±1)

[figure not shown]
- Subject will arrive after wearing lenses for at least 5 hours.
- Monocular logMAR visual acuity will be performed.
- [Redacted]

- Lenses will be removed and retained.
- Slit lamp biomicroscopy (including bulbar and limbal hyperaemia) will be assessed using sodium fluorescein according to the guidelines set out in the CVI Grading scales (Appendix 3).
- The subject's eyes will be rinsed with saline, if requested by the subject.
- The subject may choose to wear their study lenses or habitual spectacles at the completion of the visit.
- The subject will be reminded to complete their remote questionnaires and will be reminded of the date for their next visit.

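### Section 10.3 leaves room for slit lamp tests of a lens-free Visit 1 against worn-lens Visits 2 and 3, which would reflect same-day wear and would not compare Test with Control (minor)

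*Combined protocol and SAP*

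**What the plan says.** Section 10.3 has two sentences that bear on slit lamp data. The first is a comparison between lenses: "Paired t-test may be used to compare slit lamp biomicroscopy, lens fit and subjective scores between study lens types". The second is a comparison over time, to be made where applicable: "Repeated Measures Analysis of Variance (ANOVA) or paired analysis may be used to compare the variables between study visits". The second names no variable, no pair of visits, and no choice between testing by arm, testing pooled, or testing an arm-by-visit term. Both are optional. The section sets alpha at 0.05 and promises an adjustment for multiplicity without naming the method.

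The state of the eye at each visit is set elsewhere. For Visit 1, Section 7.3.1 requires that subjects "Have not worn habitual lenses for at least 12 hours before the baseline/screening examination". Section 7.5.1 has them arrive without contact lenses and lists the slit lamp before study lenses are dispensed. For Visit 2, Section 7.5.2 states: "Subject will arrive after wearing lenses for at least 5 hours"; the lenses then come out and the slit lamp follows. For Visit 3, Section 7.5.3 states: "Subject will arrive after wearing the lenses for at least 5 hours", and Table 2 schedules a slit lamp examination there.

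Eligibility in Section 7.3.1 also includes that the subject "Is a habitual comfilcon A wearer and worn a comfilcon A lens for at least one month". On numbers, Section 10.2 gives "minimum 72 subjects (48 in test arm and 24 in control arm) to complete is required".

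**The concern.** The trial asks whether the novel process performs like the current one. A between-visit test has a different null hypothesis: no change over time. For slit lamp grades, Visit 1 differs from the later visits in two ways at once. The subject has started the study lens, and the eye has carried a lens that day. The test cannot separate the two. Subjects already wear comfilcon A, and Control is comfilcon A from the current process, so a change in the Control arm would plausibly be mostly same-day wear.

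The risk lies in interpretation. A rise in hyperaemia or staining from Visit 1 could be reported as a study-lens finding. If the tests were run by arm, a change seen in Test but not in Control could be taken as a difference between processes when the 2:1 allocation alone produced it. Section 10.4 lets the sponsor stop enrolment if the lenses appear to perform differently, without naming a measure, so it is worth closing off a misleading one.

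**Working it through.** **1. The visits side by side**

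| | Visit 1 | Visit 2 | Visit 3 |
|---|---|---|---|
| Lens state on arrival | no lenses for ≥12 h | ≥5 h of wear | ≥5 h of wear |
| Slit lamp | before study lenses go on | after lens removal | scheduled in Table 2; order of steps not visible in the public text |

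Visit 2 against Visit 3 is like for like on the wear rule. Visit 1 against either is not.

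**2. What each test estimates**

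Let w be the mean effect of same-day wear on a grade, and s_T and s_C the further effects of the Test and Control lenses.

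- Change from Visit 1 in Test: w + s_T. In Control: w + s_C.
- A within-arm visit test asks whether w + s_T (or w + s_C) is zero.
- The trial's question is whether s_T − s_C is zero. In the between-arm difference, (w + s_T) − (w + s_C) = s_T − s_C, so w drops out.

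**3. The plan's own figure**

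The only stated power is for acuity: 92% for a 0.06 difference, SD 0.06, 24 per group. A two-sided two-sample t-test has noncentrality (0.06/0.06)/√(1/24 + 1/24) = 3.46 on 46 degrees of freedom and gives 92.4%, so the figure reproduces. There is no corresponding figure for slit lamp grades.

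**4. Size, if tests were run by arm**

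Inputs:
- n = 48 and 24 (Section 10.2)
- alpha = 0.05 (Section 10.3), two-sided as in the alternative hypothesis of Section 10.1
- lenses identical, so s_T = s_C = 0
- d = w divided by the SD of the within-subject change, which is **assumed**

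A paired t-test has noncentrality d√n on n − 1 degrees of freedom. At d = 0.3 this is 0.3 × √48 = 2.08 for Test and 0.3 × √24 = 1.47 for Control. The arms are independent, so the chance of Test only is P(Test) × [1 − P(Control)]; at d = 0.3, 0.530 × (1 − 0.291) = 0.376.

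| d | Test, n=48 | Control, n=24 | Pooled, n=72 | Test only | Control only |
|---|---|---|---|---|---|
| 0 | 5% | 5% | 5% | 5% | 5% |
| 0.2 | 27% | 16% | 39% | 23% | 11% |
| 0.3 | 53% | 29% | 71% | 38% | 14% |
| 0.4 | 78% | 47% | 92% | 41% | 10% |
| 0.5 | 92% | 65% | 99% | 32% | 5% |
| 0.8 | 100% | 96% | 100% | 4% | 0% |

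A simulation of 40,000 trials at d = 0, 0.3, 0.5 and 0.8 agrees with the within-arm and discordance columns.

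**5. With a multiplicity adjustment**

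The method is not named, so assume Bonferroni over three visit pairs: 0.05/3 = 0.0167. Test vs Control becomes 15% vs 7% at d = 0.2, 35% vs 15% at 0.3 (0.352 vs 0.155) and 62% vs 29% at 0.4 (0.615 vs 0.289). Test-only discordance falls to 14% at d = 0.2 and 30% at 0.3, but is 44% at 0.4. Adjustment changes the rates without removing the imbalance.

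**6. The between-arm alternative**

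In the same simulation, a two-sample t-test of change between arms rejected in 5.1%, 5.1%, 5.1% and 4.9% of trials at d = 0, 0.3, 0.5 and 0.8. A separate simulation on an assumed 0–4 grade scale (4,000 runs per shift, latent correlation 0.5 between visits) gave 4.9% to 5.5% for a between-arm comparison adjusted for the Visit 1 grade.

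**The case against.** The strongest reply is that 10.3 does not commit to the test in question. The sentence is optional, does not name slit lamp, does not name Visit 1, and does not say that tests are run by arm. A reader might infer that the plan will judge the process by setting a significant Test-arm change against a non-significant Control-arm change. Nothing in the documents says so, and the hypothesis in Section 10.1 is between arms. This stands, and it is why the Test-versus-Control rates are conditional.

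A reader might also infer that 10.3 offers no between-lens comparison of slit lamp grades. It does, in the sentence just before. That comparison is intended but cannot be carried out as written: Test and Control are worn by different subjects, so there are no pairs between lens types. The reply therefore stands on intent, and the fix has to cover that sentence too.

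Third, if wear does shift grades, rejecting no change is a correct result. This also stands. The percentages above are power against an assumed real shift, and the error would lie in attributing that shift to the study lens.

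Fourth, the sizes are assumed throughout, and they treat grades as continuous. The grading scale is not visible in the public text. On the assumed 0–4 scale, pooled visit tests rejected in 32%, 61% and 85% of runs at latent shifts of 0.2, 0.3 and 0.4, somewhat below the tabulated pooled values, although the two shift scales are not identical.

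Finally, change from a lens-free baseline has its own descriptive use, and adverse event codes 15 and 22 in Section 8.1 rely on grade change from baseline. Nothing here argues against showing those changes or applying those codes.

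**Conclusion.** The point holds as a gap in the wording. Section 10.3 permits a slit lamp test of Visit 1 against Visit 2 or 3, and such a test would reflect same-day wear as well as any study-lens effect. That follows from the visit rules and needs no assumption about size.

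The excess of significant results in Test over Control needs two further conditions: testing separately by arm, which 10.3 neither states nor rules out, and a wear effect above zero, which the documents do not give. With no wear effect, both arms are at 5%. With a pooled visit test the imbalance between arms does not arise, although the confusion of wear with lens remains.

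The point is minor. A reader might infer that it threatens the main conclusion. It does not: the primary endpoint is 4-week logMAR acuity, hypothesised between arms and measured under the same 5-hour wear rule in both, and the synopsis lists no secondary outcomes.

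**What to change.** In Section 10.3, for slit lamp variables, replace both the paired t-test between lens types and the between-visit test, so that the section does not hold two conflicting analyses. Suggested text:

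> Slit lamp grades at Visits 2 and 3 will be compared between Test and Control, adjusted for the Visit 1 grade, for example in a repeated-measures model with lens type, visit, lens type by visit and Visit 1 grade. Changes within each arm from the lens-free Visit 1 will be presented descriptively. Separate within-arm p-values will not be used to compare the lenses.

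The visit and lens-type-by-visit terms still allow Visit 2 and Visit 3, which share the wear rule, to be compared.

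The cost is wording only. The grades are already scheduled at all three visits, so no subjects, visits or procedures are added. The small downside is that there would be no within-arm p-value for change from baseline.
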